# Side effects

We will collect data on the following potential side effects of lefamulin and of doxycycline through our electronic REDCap surveys upon completion of the regimen and at 21-28 days and at 42-47 days after completion of the regimen.

- Gastrointestinal complaints: diarrhea, nausea, vomiting
- Other systemic complaints: photosensitivity, excess vaginal yeast with itching
- Other (open text field for patients to record other events)

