# Inclusion Criteria:

- Physician referral
- Persistent symptomatic urogenital MG infection documented by any NAAT 14-90 days after completion of the prior antimicrobial regimen for MG
- Low risk of reinfection defined as no unprotected sex with an untreated sex partner since completion of the prior antimicrobial regimen
- Male or female sex at birth
- ≥18 years of age
- English-speaking
- Able to provide written informed consent
- Able to undergo a test to confirm MG infection at baseline and tests of cure 21-28 days and 42-47 days after completing lefamulin

- Referring physician willing and able to provide needed patient information
- Living in the US

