## Clinical, symptom, adherence, and side effects data

In addition to the CDC MG Treatment Failure CRF, the study physician will ask about other aspects of the patient medical history and enter this information into a separate UW ITHS REDCap form (concomitant medications, other relevant medical history, etc.). Where available, the study physician will also obtain Gram stain results and chemistry panel with liver function test results.

We will also program electronic surveys, using the UW ITHS REDCap platform, that will be completed by the patient on the start date of the first antibiotic course, upon completion of the antibiotic regimen (lefamulin alone or lefamulin and doxycycline), and at the 21-28-day and the 42-47-day test-of-cure timepoints. The REDCap surveys will collect information on dates of

antibiotic use, symptoms, antibiotic adherence, sexual behavior, and side effects. We will also program electronic reminders to remind the patient to complete the REDCap surveys and to mail in the test of cure and culture specimens.

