## **Outcomes**

We will assess one primary outcome and five secondary outcomes.

- Primary Outcome
  - Microbiologic cure defined as a negative Aptima MG test 21-28 days after completing lefamulin
- Secondary Outcomes
  - Microbiologic cure, as defined above, after lefamulin alone compared to microbiologic cure after sequential treatment with doxycycline followed by lefamulin
  - Clinical cure defined as absence of symptoms, absence of visible discharge, and absence of other clinical signs (<5PMNs/hpf on Gram stained smear where available) 21-28 days after completion of the lefamulin
  - Reported adherence to lefamulin (defined by self-reported number of tablets taken)
  - Reported adverse events (defined by self-reported adverse events)
  - Sustained microbiologic cure defined as a negative Aptima MG test 42-47 days after completing lefamulin

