# Data analysis

We will calculate and present simple proportions and 95% CIs for each of our outcomes. We will not require complete data on all outcomes to be included in analyses. Instead, the denominator will be the total number of patients for whom we have complete outcome data for the outcome of interest. For example, patients with test of cure data but without clinical cure data will be included in the calculation of microbiologic cure but excluded from the calculation of clinical cure.

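### The side-effect checklist has no stated pre-dose reading and an adverse event need not be new or worse, so complaints that predate treatment may be counted

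*Combined protocol and SAP*

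**What the plan says.** Four sections of the combined protocol and SAP bear on this point.

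- **Side effects** lists the complaints to be asked about: three gastrointestinal items, photosensitivity, vaginal yeast with itching, and an open-text field. Its schedule reads: "We will collect data on the following potential side effects of lefamulin and of doxycycline through our electronic REDCap surveys upon completion of the regimen". Two later collections follow, at 21-28 and 42-47 days. All three times follow treatment.
- **Clinical, symptom, adherence, and side effects data** schedules four patient surveys, the first of them "completed by the patient on the start date of the first antibiotic course". It then says that the surveys, taken together, collect dates of "antibiotic use, symptoms, antibiotic adherence, sexual behavior, and side effects". It does not say which survey asks which item.
- **Outcomes** gives the secondary outcome as "Reported adverse events (defined by self-reported adverse events". There is no requirement that the event be new or worse since the first dose, and no attribution rule.
- **Data analysis** states "We will calculate and present simple proportions and 95% CIs for each of our outcomes", with no baseline adjustment.

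The patients are symptomatic at entry. The inclusion criterion reads "Persistent symptomatic urogenital MG infection documented by any NAAT 14-90 days after completion of the prior antimicrobial regimen for MG".

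**The concern.** An adverse-event proportion is read as what the regimen did to patients. To support that reading, the plan needs either a pre-dose answer to the same questions or a definition that excludes complaints already present. The Side effects schedule provides no pre-dose time and the Outcomes definition makes no exclusion.

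The population makes this more than a formality. Everyone enrolled has a symptomatic urogenital infection. One checklist item, vaginal itching, can overlap with genital symptoms, and the open-text field can take any complaint. Both regimens contain active drug, so no untreated arm shows the background rate.

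What is at stake is the absolute adverse-event proportion, a listed secondary outcome intended for a sponsor report and a publication. Any error from this source runs upward, and the confidence interval does not reflect it. If the listed complaints are not recorded before dosing, a contemporaneous baseline cannot be obtained later.

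**Working it through.** **1. Schedules side by side**

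| Time | Patient survey scheduled? | Checklist named in Side effects? |
|---|---|---|
| Start date of first antibiotic | Yes | No |
| End of regimen | Yes | Yes |
| 21-28 days after | Yes | Yes |
| 42-47 days after | Yes | Yes |

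The first row is the only mismatch. The survey section lists symptoms and side effects as content of the surveys as a group, so the start-date survey may or may not ask about them. The study physician takes medical history and concomitant medications before prescribing, but no pre-dose recording of the listed complaints is described.

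**2. Would a baseline answer be used if it were collected?** Not under the current text. Outcomes does not refer to it and Data analysis does not adjust for it.

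**3. Which items are exposed?**

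- Vaginal itching, in female patients only, and open-text entries are the plausible overlaps with urogenital infection.
- The documents do not describe diarrhea, nausea, vomiting or photosensitivity as symptoms of the infection. For these the route would be carry-over from the prior antibiotic, which is weaker. The 14 days in the inclusion criterion is the minimum to the qualifying test. Referral, consent, pharmacy preparation and mailing come between entry and the first tablet.

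**4. Illustration of size**

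The plan states no adverse-event figure, so there is none to reproduce. Neither input below is in the documents; both are assumptions.

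- t = true proportion with a new event, set at 20%
- b = proportion with a pre-existing complaint that is later reported, from 0% to 20%

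Taking the two as independent, reported proportion = b + (1 − b) × t.

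- b = 0%: 0 + 1.00 × 0.20 = 20%
- b = 5%: 0.05 + 0.95 × 0.20 = 24%
- b = 10%: 0.10 + 0.90 × 0.20 = 28%
- b = 20%: 0.20 + 0.80 × 0.20 = 36%

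The upward shift is b × (1 − t), or 0, 4, 8 and 16 percentage points. If only half of a 10% background were later reported, the effective b would be 5% and the result 24%. With b = 10%, t = 10% gives 19% and t = 30% gives 37%.

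**5. Against sampling error**

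Exact (Clopper-Pearson) limits reproduce Table 2 of the Sample size section; for example, 17 cures in 20 gives 62.11-96.79%. By the same method, for an arm of 20 with complete data:

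- b = 0%: 20% is 4/20, 95% CI 5.7-43.7%
- b = 10%: 28% of 20 is 5.6, taken as 6/20, 95% CI 11.9-54.3%

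The illustrative shift of 8 points is well inside an interval about 38 points wide (43.7 − 5.7).

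**The case against.** The strongest objection is that the survey section lists symptoms and side effects for surveys that include the start-date one. A baseline may therefore already be planned, and the text does not show that side effects are asked about only after treatment. That stands as far as it goes: the sections are unaligned and an omission is not proved. It does not settle the matter, because Side effects gives specific times without a pre-dose one, and neither Outcomes nor Data analysis would use a baseline answer.

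A reader might go further and infer that leftover complaints will be counted and can never be removed. The documents do not support this. The survey questions are not given. The items are presented as potential side effects of the drugs, so patients may report only what began with treatment. If symptoms are recorded on the start date, some pre-existing complaints could be identified afterwards.

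A reader might also infer that patients start treatment 14 days after another antibiotic and so carry over its gastrointestinal effects. The 14 days runs to the qualifying test, with further steps before dosing, and nothing in the documents shows that diarrhea is present at entry.

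Two limits on the consequence also stand. While both arms are randomized, pre-existing complaints should balance on average. That protects a between-arm contrast, but the only such contrast listed under Outcomes is for microbiologic cure, and randomization does not correct an absolute proportion. The illustrative shift is also smaller than the interval width, although it is one-directional and a wide interval does not remove it.

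**Conclusion.** The concern holds in a limited form. Followed as written, the plan allows complaints present before the first tablet to enter the crude adverse-event proportion, most plausibly vaginal itching and open-text genital symptoms, and less plausibly the gastrointestinal items. It does not establish that this will happen.

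The size cannot be computed, because no baseline rate is given. The 20% to 36% range rests on an assumed new-event rate of 20%, an assumed background of 0% to 20%, independence, and every pre-existing complaint being reported later. The result could be no shift at all.

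The effect is confined to the absolute rate of one descriptive secondary outcome. Microbiologic cure, the futility rule and the sample size are untouched. This is an inexpensive improvement to make before enrollment, not a flaw that threatens the trial.

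**What to change.** 1. In **Side effects**, add the start date to the collection times, with the same checklist and open-text field answered before the first tablet of either drug, in the survey already scheduled.
2. In **Outcomes**, define the adverse-event outcome as a listed or other event that is new, or reported as worse, compared with the start-date answer. Report the crude proportion of any self-reported event alongside it.
3. State the recall period for each survey and make the baseline period comparable with follow-up. The documents give none, and the end-of-regimen survey covers 7 days of treatment with lefamulin alone but 14 with sequential therapy (7 + 7).
4. In **Clinical, symptom, adherence, and side effects data**, say which survey asks which items, so that this section, Outcomes and Side effects agree.

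The cost is a short checklist added to an existing survey, a sentence or two in the text, and slightly more patient time on day 1. Sample size, specimens and treatment do not change.

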## Enrollment and consent

After the referring provider obtains verbal consent from their patient to contact the study team, the study physician will conduct an initial telephone or zoom consultation with the referring provider to discuss the patient's case and to determine initial eligibility. The study physician will complete the case report form (CRF) as a UW ITHS REDCap form, the referring provider will

indicate that verbal consent was obtained in a UW ITHS REDCap form, and sign and date the form. The CDC has developed an MG Treatment Failure Case Report Form (CRF) to document and track treatment failures that was approved by the OMB in March 2021. We propose to use this CRF to document cases of treatment failure, allowing us to link with the eventual CDC process for tracking MG treatment failures. The study physician will abstract information on concomitant medications, and other relevant medical history, to confirm eligibility and enter this information into a UW ITHS REDCap form. Where available, the study physician will also abstract Gram stain results and chemistry panel with liver function test results.

Upon receipt of the CRF, a research coordinator will arrange a zoom discussion between the study physician and the patient to explain the study procedures, answer questions, and obtain written informed consent, using the UW ITHS REDCap electronic signature process for consent. The UW-ITHS-supported version of REDCap meets the FDA's Part 11 electronic system requirements. The additional clinical information and the CRF will be completed by the study physician during the discussion with the patient to confirm eligibility and prior to prescribing lefamulin (and doxycycline for patients randomized to sequential therapy).

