#### Dispensing lefamulin (and doxycycline, as warranted)

[name] will be the prescribing physician of record and partner with the UW Harborview Medical Center Investigational Drug Services (HMC IDS) to check for drug interactions and/or contraindications to lefamulin (and doxycycline for patients randomized to sequential therapy). Lefamulin and doxycycline will be stored in and dispensed from the UW HMC IDS Pharmacy, which will serve as the pharmacy of record. This is a locked, temperature-controlled facility adjacent to the PHSKC Sexual Health Clinic that manages and dispenses all medications for research studies conducted at the Harborview campus. HMC IDS will be responsible for tracking, documentation, and return/disposal of any unused drug provided by Nabriva.

Upon receipt of a prescription from [name], HMC IDS will prepare the medication packet(s). The research coordinator will ship the medication packet(s) to the patient. Mailing antibiotics across state lines is permissible with an IND exemption in place, which is the case here. Per our consultation with a clinical trials pharmacist, "when a clinical study is found to be IND exempt [21 CFR 312.2(b)], the FDA has granted that study the same permissions as a study with an IND (such as placing investigational drug into interstate commerce). ... with a documented IND exemption, ... the drug can be shipped across state lines when a subject has been enrolled in the study [21 CFR 312.40]." (full text of letter noting on file in the regulatory binder). The FDA has granted this study an IND exemption, cross-referencing Nabriva Therapeutics' existing IND. In addition to the lefamulin tablets, the medication package will include a drug information sheet for lefamulin; contact information for any patient questions about the antibiotic, side effects, or both; a letter, which provides an overview of the study; a specimen collection instruction sheet for each specimen; a return shipment instruction sheet; and materials for patients to collect and return two specimens (one specimen for culture and assessment of MICs; the other specimen to confirm MG infection at baseline). For patients randomized to sequential therapy, the medication package will also contain doxycycline tablets and a drug information sheet for doxycycline.

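### In Regimen B no described step asks about new medicines before lefamulin starts on about day 8, and the prompted side effects name no cardiac, hepatic or allergic-rash symptom

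*Combined protocol and SAP*

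**What the plan says.** The Exclusion Criteria bar patients with known QT prolongation or ventricular arrhythmia, those on other QT-prolonging drugs (erythromycin and moxifloxacin are among the examples), those on various CYP3A or P-gp inducers and inhibitors, and those with liver disease or a known allergy to the study drugs.

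The checks against these criteria are described in two places. Under Enrollment and consent: "The study physician will abstract information on concomitant medications, and other relevant medical history, to confirm eligibility". The talk with the patient that confirms eligibility also comes before either drug is prescribed. Under Dispensing lefamulin (and doxycycline, as warranted), the prescriber works with the investigational pharmacy "to check for drug interactions and/or contraindications to lefamulin" and, where assigned, to doxycycline. For Regimen B, "the medication package will also contain doxycycline tablets and a drug information sheet for doxycycline", so both drugs leave in one shipment. Each package also holds a lefamulin information sheet and "contact information for any patient questions about the antibiotic, side effects, or both".

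From then on the described data collection is by REDCap survey, "completed by the patient on the start date of the first antibiotic course, upon completion of the antibiotic regimen", and again at the two test-of-cure times. The surveys gather dates of "antibiotic use, symptoms, antibiotic adherence, sexual behavior, and side effects". The Side effects section gives the prompts: diarrhea, nausea and vomiting; then "Other systemic complaints: photosensitivity, excess vaginal yeast with itching"; then "Other (open text field for patients to record other events". No ECG is described, and liver tests are collected only where they already exist.

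**The concern.** The plan treats a concurrent QT-prolonging or interacting medicine as a reason not to give lefamulin. That status can change after screening. Patients stay under the care of their own providers across the country, receive the drug by mail, and in Regimen B hold the lefamulin for a week before they are due to take it. If one of them starts an excluded medicine in that week, nothing described would bring it to the study physician's notice before the first lefamulin tablet.

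The second part concerns data. Reported adverse events are a secondary outcome. The symptoms that correspond to the plan's own cardiac, hepatic and allergy exclusions are not prompted, so they are recorded less reliably than the five that are. With no ECG and no required liver test, what the patient reports is nearly all the safety information the trial will have.

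**Working it through.** The plan states no figure on this point. The check is a dosing calendar, a count of patients and a comparison of the listed content.

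**1. Calendar.** Study Design gives 7 days of lefamulin in Regimen A, and 7 days of doxycycline followed by 7 days of lefamulin in Regimen B. Let day 1 be the first dose of any study drug, and let *s* be the days from the dispensing check to day 1 (preparation, shipping and any wait). The documents do not give *s*.

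| | Regimen A | Regimen B |
|---|---|---|
| Start-date survey | day 1 | day 1 (doxycycline) |
| First lefamulin dose | day 1 | day 7 + 1 = 8 |
| Last lefamulin day | day 7 | day 7 + 7 = 14 |
| Completion survey | about day 7 | about day 14 |
| Age of last check at first lefamulin dose | *s* | *s* + 7 |

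Whatever the value of *s*, the check is at least 7 days old in Regimen B. No survey falls between day 1 and about day 14 in that arm, so none coincides with the switch. The two later surveys come at least 21 days after lefamulin ends.

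**2. Patients assigned to Regimen B.** The first 20 patients are randomised 1:1, which gives 20 / 2 = 10.
- Regimen B dropped, or both regimens stopped, at the interim: 10.
- Both continue: 20.
- Regimen B alone retained: 10 + 20 = 30.

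Fewer would reach the switch if some stop during doxycycline.

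**3. Is there a second check?** A second dispensing of lefamulin would trigger a second pharmacy review, but the single package rules that out. The listed survey topics are dates of antibiotic use, symptoms, adherence, sexual behavior and side effects. Other medicines are not listed. Concomitant medications appear only in the forms the study physician completes from the medical history.

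**4. Prompted symptoms.** Five items: diarrhea, nausea, vomiting, photosensitivity, and vaginal yeast with itching. Items naming a cardiac, hepatic or allergic-rash symptom: 0 of 5. Nausea and vomiting can accompany liver injury, but they are non-specific and are listed as gastrointestinal. Photosensitivity is not a prompt for allergic rash. The Side effects section first collects these items on completion, after the last lefamulin tablet in either arm. Better prompts there would improve recording. They would not stop a dose.

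**The case against.** The strongest objection is that this argues from documents we have not seen. The survey forms and information sheets are not in the file, and the consent pages were removed from the review copy. A warning not to start other medicines would naturally sit in one of them. The plan also gives patients a contact for questions and names the referring provider as the official point of contact. This stands as a limit: the point covers only the steps the plan describes. But a sheet or a phone number relies on the patient to recognise the problem, and no follow-up duty is stated for the provider.

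It is also fair that exclusion criteria are not a list of expected adverse events, and that the Background reports lefamulin as well tolerated. The choice of symptoms to prompt is partly judgement.

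Three stronger readings are tempting, and the documents do not support them:
- **All the QT, liver and allergy exclusions need rechecking.** These are criteria of known history or standing impairment and are unlikely to change in a week. New medicines are what plausibly change. In Regimen A the exposure is only the mailing gap.
- **Cardiac, hepatic or rash events can reach the data only through free text or a patient's call.** The surveys also have a separate symptoms topic whose items are not defined, so the most that can be said is mainly.
- **The futility set must be redefined so that a withheld patient is replaced.** If one of an arm's ten were an automatic non-cure, the chance of dropping a regimen with true 60% cure would rise from P(X ≤ 3 | n = 10) = 0.0548 to P(X ≤ 3 | n = 9) = 0.0994. But limiting the ten to patients who started lefamulin selects on an event after randomisation that is likelier in Regimen B. It would also remove patients who stop during doxycycline, and so favour that arm. The plan as written has no withholding step, so it does not itself create this problem.

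**Conclusion.** The point holds as a low-cost improvement. It is not a defect that undermines the trial. As described, a Regimen B patient could start lefamulin on about day 8 alongside a medicine the plan excludes, at least 7 days after the last check, without being asked. Between 10 and 30 patients are assigned to that regimen. None of the five prompted side effects names a cardiac, hepatic or allergic-rash symptom.

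The conclusion assumes that the surveys contain what the plan lists and no question on new medicines. If the forms already ask, the protocol need only say so. The documents give no rate of new interacting medicines, so no expected number of overlaps or events is claimed. Confidence is medium because the forms were not seen. A reader might infer that added prompts would establish cardiac or hepatic safety. They would not, in a trial of 40. The gain is protection of individual patients and better symptom recording.

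**What to change.** 1. Ask whether any new medicine has been started since screening, to be answered before the first lefamulin tablet. In Regimen A, put it in the day-1 survey and state that it comes before the tablet, since a survey completed on the start date could otherwise follow it. In Regimen B, send one automated REDCap prompt at the switch. If the answer is yes, tell the patient to contact the study team before starting lefamulin. The study physician then decides whether to proceed.
2. Add four prompted items to the existing completion and follow-up surveys: palpitations; fainting or light-headedness; yellow skin or dark urine; rash.
3. Report any patient whose lefamulin is withheld, by arm and with the reason. Leave the futility rule and its first-ten set unchanged.

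The cost is one question, four symptom items, one automated prompt in Regimen B on a platform that already sends reminders, and a brief physician review of each yes. Reported side-effect rates may rise slightly. A rare patient may have lefamulin delayed or withheld, more likely in Regimen B because of the extra 7 days. An unanswered prompt leaves the patient as the plan does now. No change to sample size or visits is needed.
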